# **Section 4:** General points for statistical analysis

#### 4.1 General considerations

All summaries and listings will be presented by treatment group.

Continuous variables will be summarized using the number of observations (n), mean, standard deviation (SD), median, minimum, and maximum. Categorical variables will be summarized using numbers and percentages. The number of missing values will be presented in summary tables.

Unless otherwise specified, the estimated mean and median for a set of values will be reported to 1 more decimal place than the original values, and standard deviations will be reported to 2 more decimal places than the original values. The minimum and maximum will report the same number of decimal places as the original values. Percentages will be displayed with 1 decimal place; percentages will not be presented when the number is zero; 100% will be presented as an integer.

All data will be listed. Data listings will be presented by treatment group.

All statistical analyses will be performed using SAS® Version 9.4 [11] or STATA 15 [12].

#### 4.2 Missing data

No imputations will be made for missing data, except in case of missing scans which are addressed in Appendix C.

# **Section 5:** Subject disposition

The following will be tabulated over all screened subjects (the number of subjects in the screened set will be used as the denominator in the calculation of percentages):

- Number of subjects screened
- Number (% of screened) of subjects randomized into the Main Investigational cohort (ITT population)
- Number (% of screened) of subjects randomized into the Pseudo-progression cohort
- Number (% of screened) of subjects entered into the Informational cohort

#### Split by treatment group for the ITT population:

- Number (% of randomized) of subjects who complete the study follow-up
- Number (% of randomized) of subjects who withdraw, by reason
- Number (% of randomized) of subjects who crossed over following progression
- Number (% of randomized) of subjects in the PP population

#### Split by treatment group for the PP population:

- Number (% of randomized) of subjects who complete the study follow-up
- Number (% of randomized) of subjects who withdraw, by reason
- Number (% of randomized) of subjects who crossed over following progression

#### Split by treatment group for the Pseudo-progression cohort:

- Number (% of randomized) of subjects who complete the study follow-up
- Number (% of randomized) subjects who withdraw, by reason
- Number (% of randomized) subjects who crossed over following progression

#### All subjects in the Informational cohort:

- Number (% of randomized) of subjects who complete the study follow-up
- Number (% of randomized) subjects who withdraw, by reason

A CONSORT diagram will be produced.

# Section 6: Demographics, other baseline characteristics, medications

Demographics and baseline characteristics such as age, extent of resection, and performance status are known prognostic factors for patients with GBM. In addition, methylation of the MGMT gene promoter is a predictive factor for response to temozolomide therapy, and other factors such as IDH-1 and -2 mutation status, 1p19q co-deletion, genetic markers such as EGFR mutations, amplification status and PTEN mutations may also contribute to outcomes in this disease. Factors such as these will be considered when interpreting the trial endpoints, as described below. All analyses and assessments will be done on both an ITT population and PP population basis, although formal claims will be made on an ITT population basis.

#### 6.1 Demographic and other baseline characteristics

Demographics (age, gender, race), baseline MGMT status, IDH mutational status, extent of resection, and Karnofsky performance status will be summarized overall and by treatment group. Distributions of treatment group data will be compared via a t-test (age) or a chi-squared test; p values will be reported for information only, to allow an assessment of the balance between the randomized groups.

Genetic markers including EGFR and PTEN status, and chromosomal abnormalities including 1p19q deletions will likewise be summarized overall and by treatment group.

#### 6.2 Medical history and concomitant diseases

Medical history summaries will be presented overall and by treatment group. Each subject will be counted only once in each category. Concomitant diseases will be identified as those flagged as 'ongoing' and will also be summarised separately.

In addition, oncological history will be summarised.

#### 6.3 Prior and concomitant medications

Prior and concomitant medications will be presented for the safety population by ATC level 2 (therapeutic main group) and ATC level 5 (standardized medication name) with numbers and percentages for each treatment group and overall. A subject who took more than one medication will be counted only once if these medications belong to the same ATC level 5 classification.

Prior medications will be defined as those medications started prior to the administration of study drug on Day 0. Concomitant medications will be defined as those medications taken following the first administration of study drug on Day 0. Hence medications started before study dosing, but continuing after, are considered as both prior and concomitant medications. The listing of medications will identify prior and concomitant medications.

Job Number: 1555

If either the start or stop date of medication is missing, the worst or most conservative case will be considered when assigning medications to categories. For a missing start date (where stop date is after date of first dose) the date will be imputed as the date of first dose; for a missing stop date the date will be imputed as the date of last dose or start date if start date is after last dose. If a partial date is recorded, the following convention will be used to assign the medication:

If a partial date is missing a start day and the month/year is the same as first dose date then use first dose date, or else '01' will be used for the day; if a start date is missing a month and the year is the same as first dose date then use first dose date, or else January will be used for the start month.

If a partial date is missing a stop day and month/year is same as the last dose date then use the last dose date, or else the last day of the given month will be used for the stop day; if a stop date is missing a month and the year is the same as last dose date then the last dose date will be used, or else December will be used for the stop month.

#### 6.4 Current disease and therapy

The parameters that will be evaluated include but are not limited to the following:

#### Disease:

- Tumor size and characteristics, such as GBM subtype, histological stage of GBM, genetic, proteomic and molecular profile
- Immunoscore
- Leukocyte measures including but not limited to:
  - Absolute lymphocyte count
  - Absolute and % T cell count
  - Absolute and % CD4+ T cells
  - o Absolute and % CD8+ T cells
  - o Absolute and % NK cells
  - Neutrophil: lymphocyte ratio
  - o T-regulatory cell count
  - o MDSC count
  - TDL+ monocyte count
- Immune checkpoint and checkpoint ligand expression
- Liquid biopsy measures, including but not limited to CTCs, CTDNA, EVs and others
- Biomarkers
- Blood characteristics

#### Co-morbidities

#### Therapy:

- Extent of resection (complete/ partial and significant residual /minimal residual)
- Radiation therapy number of sessions and total dose
- Concomitant temozolomide dose per day / days

Job Number: 1555 Customer Reference: Study ID: 020221 SAP Version: 1.0

Adjuvant temozolomide dose per day / days and months

- Number of DCVax®-L doses
- Steroid therapy dose per day / days
- Concomitant medications

# **Section 7:** Exposure

The scheduled dosing regimen in the double-blind period comprises 10 administrations. However, some participants in the DCVax®-L treatment arm may not receive 10 immunizations due to insufficient manufacturing material (Protocol Section 3.3) or otherwise. The intended number of cells for each treatment is 2.5 million cells (two injections of 1.25 million cells). The volume of study drug for delivery of that number of cells is participant-specific (Protocol Section 8.1).

Further, all participants in both treatment cohorts whose disease progresses, as defined in Section 15.2 of the protocol, were offered a crossover option at the time of disease progression. All the participants from either arm of the trial who elected to receive DCVax®-L in the crossover, will have re-started the original 10-administration schedule using DCVax®-L, with all parties (patient, investigator, CRO and sponsor) remaining blinded to the patients' original randomized allocation.

For all subjects in both treatment cohorts, the following exposure variables will be calculated for the initial trial period and the crossover period:

- Number of DCVax®-L administrations
- Total number of cells received per administration
- Total number of cells received overall

These will be summarized as continuous variables, by treatment group and overall.

The numbers and percentages of subjects who receive at least 3 administrations, and who receive at least 6 administrations, will also be summarized as categorical variables by treatment group and overall.

# **Section 8:** Efficacy

In the analyses described below, the following methods will be used for confidence interval calculation:

- Hazard ratio: Wald method
- Median survival: Brookmeyer and Crowley method
- Landmark survival probabilities: Hall-Wellner method (calculated on the log scale and back transformed)

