#### 1.2.1 Primary endpoint: OS compared with external controls – 3 analyses

**Analysis #1: Overall survival in the whole patient population**: This analysis will evaluate the overall survival curves and median survival for all of the patients in the Trial (both ITT and PP populations). This analysis will compare the survival times of the 232 patients initially randomized to DCVax®-L to the selected external controls. The comparisons will include the following:

- an overall comparison of the 232 patients to all external control patients, pooled;
- a matching-adjusted indirect comparison (MAIC) that takes into account the distribution of prognostic factors between the 232-patient DCVax®-L trial population and the external controls, pooled;
- a MAIC of the 232 patients to the control patients of each individual external control trial.

All comparisons will include an overall curve comparison, as well as comparisons of survival percentages at certain time points (so-called milestone analyses).

Analysis #2: Conditional survival -- the "long tail": This analysis will evaluate specifically the "long tail" of survival in patients treated with DCVax®-L in this Trial. With immunotherapies, one of the features most focused upon and considered most important clinically is their capability to deliver greatly extended survival in a percentage of patients. This analysis will apply an established statistical methodology – conditional survival – to evaluate the survival tail in this Trial separately from the larger picture. This methodology will evaluate all of the survival data relating to patients who survived beyond a specified time threshold. (This time threshold is the "condition" or trigger of the analysis). By analysing all of the data from the time threshold onwards, this methodology evaluates the whole survival tail and provides a more complete and representative assessment than a landmark analysis which would only evaluate the status of the survival tail at a specific time point.

**Analysis #3: Survival in pre-specified sub-groups:** It has become well recognized that GBM patients may be categorized into distinct sub-groups based upon certain patient characteristics and/or tumor characteristics, and these distinct sub-groups have materially different survival with GBM. Such

SAP Version: 1.0

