#### 1.3.2 Sample size for OS

The implication of this sample size of 348, accrued as described above, for the OS endpoint is as follows. We assumed median OS of 17 months among subjects in the placebo arm, and set the type I error rate for this analysis to 0.025, one-sided. To detect the expected benefit of 8.3 months' increase in median OS (to a median of 25.3 months) in the DCVax®-L arm would require an extension of the follow up time to 36 months after completion of enrolment. Then the power of the log-rank test is approximately 80.5%. The corresponding number of events is approximately 233.

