#### 8.1.3 External studies in newly diagnosed GBM

A systematic literature review has been conducted by independent experts to identify appropriate studies in newly diagnosed GBM to provide the external controls. This selection of studies has subsequently been reviewed by independent key opinion leaders in the field who were not involved in conducting the Trial, and has received their support. The five studies shown in Table 3 [6, 13-16], which were conducted in similar populations as in the current Phase III study, each with a control arm treated with the standard radiotherapy and temozolomide regimen, will be included. It is possible that additional studies may be added, e.g. with the goal to provide a larger population of patients with long (e.g.  $\geq$  4 years) follow-up times. In addition, a MAIC will be undertaken to ensure matching of the Trial subjects and the external controls.

It is recognized that each of these studies had unique inclusion and exclusion criteria, and that no single study can provide a perfectly matched control population. Nevertheless, the distribution of known prognostic factors between the enrolled patient populations reveal that these populations were similar in composition, and in fact the study outcomes are also remarkably similar: These five studies selected by the independent expert review provide 1,366 patients for the combined control group in total.

Median overall survival for these 1,366 patients is 16.5 months, with a 95% confidence interval of 16.0 to 17.5 months, demonstrating that outcome in this disease is highly consistent and predictable.

The Gilbert et al. (2014) study randomized patients 3 weeks prior to completion of chemoradiation therapy, and if that study is excluded from the analyses the outcomes of the control subjects are as follows: n=1,057; mOS=16.8 months (95% CI: 16.1-17.7 months).

Page 33 of 57 Confidential

Table 3: Studies selected providing comparable control arms

[figure not shown]
Lead	Year	Journal	CONT	ROL GROUP		
author			Treatment	N	Median OS (months)	OS Kaplan-Meier curves available for subgroups
Gilbert	2013	JCO	XRT + temozolomide	411	16.6	MGMT methylated (N = 122), unmethylated (N = 254)
Stupp	2017	JAMA	XRT + temozolomide	229	16.0	Age < 65y (N = 184), Age ≥ 65 y (N = 45),  MGMT methylated (N = 77),  unmethylated (N = 95)
Weller	2017	Lancet oncology	XRT + temozolomide	374	17.4	Minimal residual disease N = 210), Significant residual disease (N = 163)

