#### 8.1.4 Comparison of treatments: if original data are available for external studies

For each study where the original IPD are available, a Cox proportional hazards regression will be conducted comparing the pooled control groups from the external studies with DCVax®-L. Covariates will be included as available. A hazard ratio and 95% confidence interval will be determined.

Kaplan-Meier estimates of the survival functions for the DCVax®-L population and the comparator population will be plotted and estimates of survival (with 95% confidence intervals) at 6, 12, 18, 24, 30, 36, 42, 48, 54 and 60 months will be calculated. Conditional survival and subgroup comparisons will be estimated similarly.

In addition, if original IPD from the comparator studies are available, a matched case-control comparison based on known prognostic factors may be feasible and may be conducted as a sensitivity analysis.

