#### 8.3.2 Analysis for OS, PFS

The intent of the original protocol was that the Cox proportional hazards model will be used for the primary analysis of OS. However the OS endpoint analysis may be confounded by non-proportional hazards due to the effects of the crossover option that was built into the protocol from the outset. Under this crossover option, all subjects from both arms of the Trial were allowed to opt to receive the active treatment DCVax®-L at the time of disease progression (measured by MRI), while remaining blinded to their initial treatment assignment. If subjects originally assigned to placebo receive treatment benefit in terms of extended survival as a result of this crossover option, then we can expect the survival curves to converge. To address possible non-proportionality while controlling type I error, a testing procedure based on a weighted log-rank statistic that was developed by Karrison will be used [28].

The intent of the original protocol was that the Cox proportional hazards model will be used for the primary analysis of PFS. When the protocol was developed in 2006 the phenomenon of pseudo-progression was largely unknown. Since then, pseudo-progression has become well recognised as a

major issue. It is now expected that, because early events specifically may not represent true disease progression, differentially in the two randomized groups, the proportional hazards assumption may not hold; the hazard ratio is expected to decrease with time as the effect of PsPD decreases.

For OS and PFS, Karrison's approach to the weighted log rank test will be used [28], based on the ITT population. A one-sided p value will be presented.

Along with the p value for the test, the hazard ratio, with a 95% confidence interval, will be presented. Estimates of 6, 12, 18, 24, 30, 36, 42, 48, 54 and 60 month OS and PFS will be provided, with 95% confidence intervals, for both randomized treatment groups.

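### Landmark survival is given Hall-Wellner limits, which form a simultaneous band for the whole curve, but the limits are reported as 95% confidence intervals at single time points

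*Combined protocol and SAP*

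**What the plan says.** The SAP opens Section 8 with a short list introduced by "the following methods will be used for confidence interval calculation". It assigns the Wald method to hazard ratios, Brookmeyer-Crowley to medians and, for survival at fixed times, "Landmark survival probabilities: Hall-Wellner method (calculated on the log scale and back transformed".

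The limits are then used at fixed months. Section 8.1.4 says that "estimates of survival (with 95% confidence intervals) at 6, 12, 18, 24, 30, 36, 42, 48, 54 and 60 months will be calculated", and Section 8.1.5 asks for the same in the primary comparison with pooled published controls. Sections 8.2.1 and 8.2.3 do so for post-progression survival. For the within-trial comparison, Section 8.3.2 says "Estimates of 6, 12, 18, 24, 30, 36, 42, 48, 54 and 60 month OS and PFS will be provided", again with 95% intervals and for both randomized groups. Table 2 lists landmarks beside the hazard ratio as an estimator for OS, post-progression OS, confirmed PFS and PFS.

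Nothing in the SAP or protocol says that the landmark limits are simultaneous, that coverage is meant jointly over the ten months, or over what time range a band would be computed.

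**The concern.** A 95% interval at one month should contain the true survival at that month in 95% of repeated trials. A Hall-Wellner band is calibrated so that the whole curve lies inside it 95% of the time. At any single month it must therefore be wider and cover more often than 95%. Its width reflects the whole curve and not only the precision at that month, so the excess is smallest near 50% survival and grows where survival is high or low.

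The other two methods in the same list give ordinary single-parameter intervals, so one 95% label carries two meanings. The Brookmeyer-Crowley interval for the median comes from inverting pointwise limits. A landmark interval could therefore contain 50% at a month that the interval for the median excludes.

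What is at stake is the reading of the milestone tables. Late landmarks would look less precise than the data make them, and readers comparing them with other trials' pointwise intervals would not be comparing like with like.

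**Working it through.** The plan states no interval width, so there is no figure of its own to reproduce.

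**Inputs from the SAP.** DCVax-L arm, n = 232 (Section 1.2.1: "This analysis will compare the survival times of the 232 patients initially randomized"). Planned DCVax-L OS: "to a median of 25.3 months" (Section 1.3.2). External controls: "Median overall survival for these 1,366 patients is 16.5 months" (Section 8.1.3). Five-year survival of 2-3% (Section 1).

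**Assumptions not in the documents.** Exponential survival where a whole curve is needed, and no censoring unless stated. The constant k = 1.358 is the 95% point of the supremum of the absolute Brownian bridge over its full range.

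**Formulas.** Let c = n × (Greenwood variance of log S). The log-scale half-widths are

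- Hall-Wellner: k(1 + c)/√n
- pointwise: 1.96 √c/√n

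Without censoring c = (1 − S)/S, so the log-scale width ratio is k/(1.96 √(S(1 − S))), whatever n is. The back-transformed limits are S·exp(±k/(S√n)) and S·exp(±1.96 √((1 − S)/(S n))).

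**Worked case, S = 50%, n = 232.** Hall-Wellner half-width: 1.358/(0.5 × 15.23) = 0.178, giving 41.8-59.8%. Pointwise: 1.96/15.23 = 0.129, giving 44.0-56.9%. Ratio 0.178/0.129 = 1.39. Coverage at that landmark is 2Φ(1.96 × 1.386) − 1 = 99.3%.

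| S (n = 232) | Hall-Wellner | Pointwise, log scale | Ratio, log scale | Ratio, back-transformed |
|---|---|---|---|---|
| 50% | 41.8-59.8% | 44.0-56.9% | 1.39 | 1.39 |
| 15% | 8.3-27.2% | 11.0-20.4% | 1.94 | 2.0 |
| 10% | 4.1-24.4% | 6.8-14.7% | 2.31 | 2.6 |
| 3% | 0.15-58.6% | 1.4-6.2% | 4.06 | about 12 |

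At S = 2% the log-scale ratio is 4.95 and the untruncated Hall-Wellner upper limit is 0.02 × exp(1.358/(0.02 × 15.23)) = 173%, above the possible range.

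**Over the ten landmarks (log-scale ratio).**

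- Planned DCVax-L OS, median 25.3 months: 1.93 at 6 months (S = 0.848), 1.39 at 24 months (S = 0.518), 1.75 at 60 months (S = 0.193). At 60 months the limits are 12.2-30.7% against 14.9-25.1%.
- External controls, median 16.5 months: 1.67 at 6 months, 1.39 at 18 months, 2.55 at 60 months (S = 0.080).

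**Simulated coverage** (n = 232, 3,000 runs, medians 16.5 and 25.3 months, with no censoring or uniform censoring between 36 and 72 months). Hall-Wellner limits covered each landmark in 99.2-100% of runs, and pointwise log-scale limits in about 94-96%. Joint coverage of the Hall-Wellner limits over the ten landmarks was 97.4-98.5%. With this censoring and the 16.5-month median, the 60-month ratio rose from about 2.5 to 3.06.

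**Sensitivity to k.** Limiting the band to the observed range lowers k by about 1% or less in most cases, and by about 3% if data stop near S = 0.4.

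**The case against.** The strongest reply is that nothing is decided on these limits. Success on the primary endpoint is judged by one-sided upper confidence limits for hazard ratios (Section 8.1.1). Within-trial OS and PFS are tested by a weighted log-rank procedure (Section 8.3.2). No landmark interval enters the fallback or gatekeeping rules, and wider limits cannot create a false claim of benefit. This stands, and it confines the point to description.

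A second reply is that simultaneous limits are valid, since they cover each landmark at least 95% of the time, and that joint coverage is a reasonable aim with ten landmarks per curve. That is true, but the SAP states no such aim. Nor are the limits tuned to ten landmarks: a Bonferroni adjustment over ten would need 2.807/1.96 = 1.43 times the pointwise width on the log scale, against 2.31 for Hall-Wellner at 10% survival.

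Two stronger readings should be resisted. A reader might infer that every landmark interval is too wide by one fixed range, such as 1.4 to 2.6. No such range belongs to the plan, because the ratio depends on survival: about 1.4 to 1.9 for the planned DCVax-L OS curve, above 4 at 2-3% survival. A reader might also infer that the long-tail claim is compromised. The formal tail analysis is conditional survival compared by a Cox model (Section 8.1.2), and Table 2 gives its estimator as the hazard ratio alone. Section 1.2.1 prefers it to a landmark analysis, and it carries 0.309% of alpha against 2% for OS in the whole population. Late landmarks would support that analysis only descriptively.

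**Conclusion.** The mismatch is real: a whole-curve band is named as the method for intervals that are reported as 95% limits at single months. Per-landmark coverage is about 99-100%. Relative to pointwise limits, the log-scale width is never less than about 1.4 times, and it increases as survival moves away from 50% in either direction. These ratios rest on no censoring and the full-range constant. Those for whole curves also assume exponential survival, and late censoring makes the last landmarks worse. The consequence is lost precision and a misleading label in descriptive tables. Type I error, power and the hazard-ratio estimates are untouched. It is worth correcting because the correction is cheap, not because any conclusion of the trial depends on it.

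**What to change.** In the Section 8 list, replace Hall-Wellner for landmark probabilities with pointwise limits from the Greenwood variance on a log-log (or log) scale. The log-log form also keeps both limits between 0 and 100%. The sections that call for 95% intervals at the ten months can then stand as written.

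The cost is one SAP line and one software option, with no change to any test. The small loss is joint coverage over the ten landmarks. If that is wanted, show Hall-Wellner limits in addition, labelled as a 95% simultaneous band with the time range over which it holds.
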